# 3. Summary

Title of study	Exploring the local operation and impact of Healthwatch in England five years on: using actor-network theory to optimise patient and public voice in NHS commissioning and service provision.
Protocol Short Title/Acronym	The local operation and impact of Healthwatch in England
Protocol version number and date	v.2 29 th September 2020
IRAS Number	252993
REC Reference	King's College London REC LRS-18/19-12587
Study duration	17/06/2019 to 31/05/2021
Sponsor name	King's College London
Chief Investigator	[name]
Funder	NIHR HS&DR
Medical condition or disease under research	Health services research
	To investigate how Healthwatch creates and sustains
Purpose of research	relationships locally with key NHS and other stakeholders as a key element of Patient and Public Involvement and Engagement.
Primary objective	The aim of the study is to explore and enhance the operation and impact of local Healthwatch in ensuring effective patient and public voice in the commissioning and provision of NHS services.
Number of subjects/patients	The total UK sample size in phase 1 (survey) is 152 local Healthwatch organisations in England.
	The total UK sample size is 5 selected organisations in phase 2 (ethnographic fieldwork). We aim to interview up to 12 participants in each study site in phase 2 (maximum = 60). We cannot estimate numbers for on-site observations in phase 2. Some of the interviewees will also take part in our Joint Interpretive Forums at each site and in the cross-site JIF in London. However, some participants might choose not to participate further.

	The total UK sample size is 15 HIP members in phase 3 (HIP member interviews/discussions regarding generalisable statements of good practice, and practices during COVID-19).
Study type	Multi-method design in four related phases: phase 1 national online survey of 152 Healthwatch; phase 2 ethnographic fieldwork at 5 local Healthwatch; phase 3 online interviews and small-group discussions with HIP members to generate statements of good practice and explore practices during COVID-19; phase 4 multi- stakeholder meetings in the format of Joint Interpretative Forums.
Endpoints	Completion of all study objectives
Main inclusion criteria	People working at or with local Healthwatch; current or former NHS patients or carers, or members of the public, who have been involved in local Healthwatch.

# 4. Summary of Research

Enabling citizens' voices to be heard is a vital part not only of planning for provision of healthcare services in a patient-centred, publicly-funded NHS but also of ensuring that the NHS is accountable to the public, communities and patients that it serves. Healthwatch was set up in 2013 with the ostensible aim of being the 'consumer champion' in health and social care in England, centrally concerned with the quality of and access to healthcare. There are 152 local Healthwatch, which are funded through local authority budgets and which have statutory powers to advise local authorities and NHS commissioners about their communities' needs and concerns relating to the provision of health and social care.

To date there is no robust, theoretically-informed, contextually-specific evidence about the processes through which local Healthwatch influence is created and maintained and how this enables more effective services. This is a significant research gap given Healthwatch's role as a key NHS partner in monitoring the quality - and supporting the development - of health and social care locally by providing NHS England and local authorities with information and advice based on the views of citizens and patients.

Employing a mixed method design, this study will produce the first generalizable evidence base of how local Healthwatch acts through mutually-influencing relations with a broad range of organisations and other stakeholders. At the heart of the study is an Actor-Network Theory (ANT)-informed ethnographic

approach which will allow us to map holistically everyday practices and the broader context in which they take place. We will do this by studying the everyday interactions between local Healthwatch bodies and a range of actors including local authorities, Health and Wellbeing Boards, residents, Trusts, Clinical Commissioning Groups (CCG), other Patient & Public Involvement (PPI) and third-sector organisations, as well as the objects (documents, reports, data and funding) that shape these interactions, to provide a detailed understanding of how these relationships are created and maintained.

The aim of the study is to explore and enhance the operation and impact of local Healthwatch in ensuring meaningful patient and public voice in the commissioning and provision of NHS services. In doing so, we aim to address the following **overarching research questions:** 

- What are the strategies, practices and structures that enable Healthwatch to enhance patient and public voice in the NHS?
- How is patient and public involvement made impactful for citizens themselves as well as commissioners, providers and other NHS actors as they are brought together through the daily work of Healthwatch?

Answering these questions will also inform the broader issue of what 'effective PPI' entails from the different perspectives of patients, commissioners, providers and other NHS actors.

To achieve our aims, the study will be organised in four phases. In phase 1 we will design and carry out a nationwide survey of the 152 local Healthwatch in England. Using the phase 1 findings to construct a sampling frame, we will then (phase 2) conduct an ANT-informed ethnographic study in five local Healthwatch. The data from this phase will be analysed in cooperation with a panel of fifteen local Healthwatch staff and volunteers (Healthwatch Involvement Panel – 'HIP' – see Box 1 below) recruited from other local Healthwatch organisations. This will ensure the generalisability of our ethnographic findings beyond the four case study sites. Based on our findings from phase 2, we will conduct a series of online interviews and small-group discussions with members of the HIP to generate emerging statements of good practice as well as exploring the impact of COVID-19 on the work of local Healthwatch during the pandemic (phase 3). In phase 4 we will hold Joint Interpretative Forums (JIF) with each case study site with multiple stakeholders (local authorities, Health & Wellbeing Boards, CCGs, CLAHRCs) engaging them in shared reflection on our findings and analysis. We will complete our interpretation of all four phases and then formulate and disseminate actionable recommendations for policy and practice.

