#### What will the HIP do?

Invited HIP members will receive one-day training in relevant qualitative methods from King's College London. HIP members will then attend 5 half-day meetings during the ethnographic fieldwork phase (Phases 2 and 3). At each HIP meeting, ethnographic data from case-study sites will be presented by research staff conducting the fieldwork. HIP members will be asked to:

- reflect on the data presented and provide interpretation and explanation based on their own experience and knowledge of working at a local Healthwatch;
- look for points of similarity and difference with their own organisational practices to help build a broader picture of local Healthwatch activity across England;
- guide the research team with detailed suggestions on how to develop the ethnographic work in accordance with short and medium-term fieldwork objectives;
- participate in a series of one-to-one online interviews and small-group discussions to generate emerging statements of good practice as well as exploring the impact of COVID-19 on local Healthwatch work during the pandemic.

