#### Sampling:

We will build our sampling strategy for the selection of five case study sites from the results and analysis of the Phase 1 survey, focusing particularly on the findings associated with variable 4, 'Jurisdictional contexts'. This choice is justified by our theoretical approach which gives prominence to the analysis of mutually-influencing relations between and among humans and nonhumans in identifying how impact is created in the daily work of local Healthwatch as it interacts with a range of other organisations. As Carter & Martin have discussed, 'local authority areas may not be coterminous with CCG or provider organisations' catchment; consequently some local Healthwatch must deal with multiple commissioners and providers that have different administrative and geographical boundaries' (14). The choice of focussing on variable 4 also addresses the expressed need to better understand how these relationships work in the context of the changing geographies of health promoted by STPs and moves towards integrating health and social care.

Focusing on this variable will allow us to select local Healthwatch based on the complexity of the jurisdictional context in which they operate and with whom they interact. This includes, for example, the number of health and social care providers, the number and type of organisations where local Healthwatch has formal representation (i.e. the number of Boards or Committees local Healthwatch participate in at Trusts, CCGs, local authorities), and the type of local authority (unitary or county). The exact nature and number of connections used to sample case study sites will be established on the basis of the results and analysis of the Phase 1 survey. We will select five local Healthwatch to be our organizational case studies which - taken together - provide a sufficiently wide range of examples of jurisdictional complexity to inform our overall findings and produce good practice for Healthwatch and other key stakeholders.

Healthwatch involvement Panel (HIP): We will invite 15 Healthwatch to participate in the HIP. The inclusion criteria are that they will have responded to the Phase 1 survey and indicated a willingness to

<sup>4 An earlier study of Health & Wellbeing Boards found differences in operation between those in unitary local authorities and those in county council areas (4).

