participate. The exclusion criteria are that they have been selected as one of the five case study sites. In the event that we receive more positive responses than needed (n=15), we will aim to ensure maximum variation of HIP members based on the same criteria used for the sampling strategy for recruitment of case study sites.

*Interviews*: During Phase 2, we will invite Healthwatch staff, volunteers, and relevant stakeholders from the five case studies to take part in individual semi-structured interviews (12 per site; 60 in total). We will aim to interview a sample of staff, managers, volunteers, local CCG members, local authorities, local Health and Wellbeing Board members and relevant provider representatives e.g. Trust patient experience managers, patients and patient organizations who are involved in the daily work of local Healthwatch.

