- to look for points of similarity and difference with their own organisational practices to help build a broader picture of local Healthwatch activity across England;
- to guide the research team with detailed suggestions on how to develop the ethnographic work in accordance with short and medium-term fieldwork objectives.

The core purpose of the HIP is to provide the basis for ensuring the ongoing generalisability of our findings.

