#### Setting/context: online/telephone interviews

Data collection: Online interviews and small-group discussions will be arranged with HIP members. For small-group discussions, we will hold online meetings for groups of 3-5 members. Based on our phase 2 findings we will create statements of good practice which we will discuss and refine through an iterative process with HIP members and through the JIFs (see phase 4 below). These statements will be generalisable though they will not all apply equally to all Healthwatch. With the help of the HIP members we will seek to advise on contexts where they might apply and work best. These statements of good practice will not necessarily be linked to the COVID-19 pandemic (although the pandemic has highlighted and catalysed existing practices and relationships which may well constitute examples of 'good practice'). We will therefore ask HIP members questions relating to the local management of the pandemic and the work and role of local Healthwatch during this time. Researchers will take notes during these sessions. Online sessions will also be recorded and transcribed by our approved transcriber.

Data analysis: We will read session transcripts and our fieldnotes. We will generate topical word codes, which will have an indexing function across the interviews and thus help us to order our analytical framework. The codes will consist of key words, concepts and ideas, some of which may be 'in vivo' i.e. provided by research participants themselves. We will place codes at the top of fieldnote entries and at appropriate points in the text as they are written at the time of our interviews; these will be refined as fieldnotes are read and re-read during data analysis. Likewise, codes will be attached to interview transcripts and documentary material. Analysis across the interviews and small-group discussions will be conducted at study team meetings and in collaboration with the Healthwatch Involvement Panel (HIP).

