# 12. Reporting and dissemination

Our research study will produce practical recommendations and actionable guidance based on formulations of good practice. These outputs will not only provide evidence based but contextually sensitive rationales for how Healthwatch might enhance patient and public voice in healthcare commissioning and provision, but also how CCGs, providers and patients can more effectively participate in these processes. The ongoing involvement of the HIP in Phase 2, their input into the emerging statements of good practice and exploration of the implications of COVID-19 on the practices of local Healthwatch in Phase 3 - together with the Joint Interpretive Forums in our case study sites in Phase 4 - will increase the likelihood of our findings and recommendations being generalizable and relevant to the way in which local Healthwatch currently operate across England.

[name] as a core team member and PPI representative will be co-authoring all outputs and dissemination activities. Patients and members of the public will be invited to the dissemination events to be held at the five local Healthwatch sites to encourage engagement with the research. We will also disseminate specifically to the Research Expert Group at St George's/Kingston University, which comprises interested members of the public and was involved at an early stage of designing our research proposal.

A range of other dissemination approaches will be used to target different audiences. We will produce a final research report for the NIHR Journals Library detailing all the work undertaken and including an abstract and executive summary focussed on findings and suitable for use separately from the report as a briefing for NHS managers. We will also prepare a set of 10 PowerPoint slides presenting the main research findings and designed for use by the research team and others in disseminating the findings to the NHS, Healthwatch and local authorities, along with an accompanying podcast series of four episodes (15 minutes) to maximise reach. The content of the podcasts will be decided towards the end of the study. Possible topics will include the range of work that local Healthwatch do, how they build relationships and how health services users and citizens can become more involved in their activities. The slides, report and podcast will be made available on the HS&DR programme website.

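### The protocol says work with the Healthwatch Involvement Panel will ensure generalisability; the design does not ensure it, and section 12 claims less

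*Protocol*

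**What the plan says.** The protocol states the same property at different strengths.

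- **Section 4, on analysing Phase 2 data with the HIP:** "This will ensure the generalisability of our ethnographic findings beyond the four case study sites". The same paragraph, and the rest of the protocol, gives five case sites.
- **Section 5.1, Phase 2, Data analysis:** "The core purpose of the HIP is to provide the basis for ensuring the ongoing generalisability of our findings". Box 1 gives the same reason for having the panel.
- **Section 5.1, Phase 3, Data collection:** "These statements will be generalisable though they will not all apply equally to all Healthwatch". The team will also seek the panel's help in advising where the statements work best.
- **Section 12:** the involvement of the HIP, together with the Joint Interpretive Forums (JIFs), "will increase the likelihood of our findings and recommendations being generalizable and relevant".

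On entry to the panel, section 5.1 (Phase 2, Sampling) says: "The inclusion criteria are that they will have responded to the Phase 1 survey and indicated a willingness to" take part. It continues: "The exclusion criteria are that they have been selected as one of the five case study sites". If more than 15 are willing, the team will aim for maximum variation on the criteria used to choose the case sites. Box 1 describes the panel as eleven staff and four volunteers from fifteen organisations.

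On the panel's work, Box 1 has members interpret case-site data and "guide the research team with detailed suggestions on how to develop the ethnographic work". Section 5.1 makes the 15 members the entire Phase 3 sample. Of that phase it says: "Analysis across the interviews and small-group discussions will be conducted at study team meetings and in collaboration with the Healthwatch Involvement Panel (HIP".

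**The concern.** A check that findings hold elsewhere is most persuasive when it comes from people who did not help to produce them. Here the group named as the basis for generalisability also helps shape the fieldwork, interprets its results, supplies all the Phase 3 data and works on the statements that come out. It can make the findings richer and better grounded. It cannot also be an independent check that they apply to other local Healthwatch.

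What is at stake is the reach of the conclusions. Objective 4 (section 4.3) promises generalisable principles, and section 12 directs the resulting good practice to national bodies, commissioners and policymakers. A reader who takes the section 4 wording at face value would give those principles more national weight than the design can support.

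**Working it through.** No sample-size formula applies: Phase 1 is descriptive and Phases 2 to 4 are qualitative. The check is a count of who is involved, a list of who does what, and a search for any later step that reaches other Healthwatch.

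**1. The protocol's own figures.** Panel: 11 + 4 = 15. Interviews: 12 × 5 = 60. Fieldwork days: 9 × 3 × 5 = 135. All agree with the text. The last two work only with five sites, so the word four in the quoted sentence is an error.

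**2. Coverage after the survey.**
- All local Healthwatch (section 5.1, Phase 1): 152, all of them surveyed.
- Panel: 15/152 = 9.9%.
- Panel plus case sites: 15 + 5 = 20, and 20/152 = 13.2%.
- Remainder: 152 − 20 = 132, and 132/152 = 86.8%.

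**3. Roles of the 15 panel members.**

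| Role | Where stated |
|---|---|
| Interpret case-site data | Box 1; Phase 2, Data analysis |
| Guide how fieldwork develops | Box 1; Phase 2, Data analysis |
| Form the whole Phase 3 sample | Phase 3, Sampling |
| Refine the good-practice statements | Phase 3, Data collection |
| Collaborate in analysing Phase 3 sessions | Phase 3, Data analysis |
| Provide the basis for generalisability | Section 4; Box 1; Phase 2, Data analysis |

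**4. When the maximum-variation rule applies.** It needs more than 15 willing organisations. With response rate *r* and willingness *w*, the pool is 152 × *r* × *w*, so *r* × *w* must exceed 15/152 = 9.9%. If all five case sites are themselves in that pool, the threshold is 20/152 = 13.2%. The protocol gives neither rate. Assuming 40% to 80% response and 15% to 50% willingness, the pool before removing case sites runs from 152 × 0.40 × 0.15 ≈ 9 to 152 × 0.80 × 0.50 ≈ 61. The rule could shape the panel substantially or never come into use.

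**5. Later steps.** Phase 4 plans five local JIFs of 8 people and one cross-site JIF of 16: 5 × 8 + 16 = 56 places. The 40 local places are tied to the case sites, as are up to 10 of the 16 cross-site places. That is up to 50 of 56. The other cross-site places are for policymakers and patient organisations. Section 12 opens the cross-site JIF to several further groups, but other local Healthwatch are not listed. The Advisory Group includes Healthwatch England and has invited Healthwatch Regional Networks, but it is not described as testing statements in other local Healthwatch. Section 12 also plans dissemination to the wider network, which comes after the principles are formed. No step puts the statements to any of the 132.

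**The case against.** The best defence is that co-production with the HIP is a deliberate choice, explained in Box 1, and that the protocol never claims statistical representativeness. Sections 4 and 4.2 also credit generalisability to the combination of methods and stakeholder engagement, not to the panel alone. Much of this stands. Case sites are chosen to span a range of jurisdictional complexity. Panel members come from other organisations and are asked to report differences as well as similarities. The protocol itself says the statements will not apply equally everywhere. These features support some analytic transferability, and 15 is not in itself too few for that purpose.

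Several stronger readings are tempting, but the documents do not support them:

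- **That the panel is simply self-selected.** The team invites members, and a maximum-variation aim applies if there is a surplus of willing organisations.
- **That the panel directs the fieldwork.** The text says it guides, through suggestions.
- **That 132 Healthwatch have no role at all.** All 152 are surveyed; the gap is in what follows the survey.
- **That members analyse one another's transcripts, which would discourage dissent.** In Phase 3 the study team reads and codes the transcripts. The panel's collaboration is on analysis across sessions, and nothing says members receive each other's interviews.
- **That confidence limits on panel agreement would measure the problem.** The protocol has no vote, rating or threshold to which such limits could apply.
- **That panel members may share an operator with a case site.** Box 4 asks whether an operator runs other Healthwatch, and the exclusion rule does not cover this, but nothing shows that it has happened.

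None of this restores the word ensure. The overlap of roles and the absence of any later check by other Healthwatch are both in the text, and section 12 already uses weaker wording.

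**Conclusion.** The concern holds as a mismatch between claim and design. The protocol says in section 4 that generalisability will be ensured, and in Phase 3 that the statements will be generalisable. The design offers interpretation by 15 organisations drawn from willing survey responders, who also help produce the findings, and no later test among the other 132 (86.8%). The supportable conclusion is that generalisability is not ensured by the design described. A reader might go further and infer that the findings cannot transfer at all. The documents do not support that, because the design has real features that favour analytic transferability.

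The coverage figures rest only on counts in the protocol. The pool range of 9 to 61 rests on assumed response and willingness rates, and the verdict does not depend on it. Separately, the number of case sites in the quoted sentence is wrong and should read five.

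**What to change.** 1. **Align the claims.** Bring section 4, Box 1 and the paragraph after it, Phase 2 Data analysis and Phase 3 Data collection into line with section 12, for example *explore transferability with 15 other local Healthwatch*. The similar sentence in section 4.2 should follow. State that analytic transferability is meant, not statistical representativeness. Correct four case study sites to five.
2. **Add one descriptive table to the report.** Show the 15 panel organisations and the five case sites against all Phase 1 responders on the variable 4 (jurisdictional context) items in Box 4, and limit the stated reach of the principles accordingly. Responders are the workable comparison group, since non-responders supply no survey data.
3. **State the limitation.** Report the panel's overlapping roles, and any operator shared between a panel organisation and a case-study site. Disclosure is enough. Box 1 already gives the panel's composition, so a new exclusion rule could mean changing an existing panel.

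Optionally, the final statements could go once to the uninvolved Healthwatch as a short online applicability rating. That would supply the missing check, at the price of one form and its response burden.

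The cost of items 1 to 3 is a less favourable claim and one extra table. The panel's co-production role and the Phase 3 coding arrangements need not change.
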